5.4 Secondary Analyses

Secondary analyses will be conducted separately for both the primary and the secondary study cohorts. All treatment group comparisons will consist of a test of the usual null hypothesis of no difference between groups; the non-inferiority hypothesis will not be tested in secondary analyses for the younger cohort.

5.4.1 Visual Acuity Defined as a Binary Outcome

Secondary analyses will estimate the proportion of subjects who achieve the following visual acuity outcomes by treatment group:

1. Amblyopic-eye visual acuity improvement of 2 or more logMAR lines (10 or more letters if E-ETDRS) 16 weeks after randomization
2. Resolution of amblyopia at 16 weeks after randomization, defined as amblyopic-eye visual acuity of 20/25 or better (≥ 78 letters) and within 1 logMAR line (≤ 5 letters) of the fellow-eye acuity.

The proportion of subjects who achieve each outcome will be tabulated by treatment group and an exact 95% confidence interval will be computed on the group proportion. A p-value for the treatment group comparison will be computed using binomial regression with adjustment for baseline visual acuity. If the binomial regression model does not converge, Poisson regression with robust variance estimation or an exact method (without baseline adjustment) will be used to derive a p-value for the treatment group comparison.

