All subjects will be seen at 4, 8, 12, and 16 weeks after randomization. Subjects achieving amblyopic-eye visual acuity equal to or better than the fellow-eye visual acuity (0 or more lines better with ATS-HOTV, or 0 or more letters better with E-ETDRS) and at least 20/25 (or ≥ 78 letters if E-ETDRS) visual acuity in both eyes will be considered to have resolved and will discontinue treatment, although these subjects will still return for all remaining follow-up exams. If at a subsequent visit there is regression of amblyopia (≥ 2 logMAR lines or ≥ 10 letters from the best previous visual acuity), treatment will be restarted.

At each follow-up visit, we will assess distance visual acuity in each eye using ATS-HOTV for children <7 years at enrollment and the E-ETDRS for children ≥ 7 years at enrollment. We will also assess stereoacuity using the Randot Butterfly Stereoacuity test and Randot Preschool Stereoacuity test, history of diplopia, and ocular alignment by cover uncover test, simultaneous prism cover test (SPCT) (if deviation present), and prism and alternate cover test (PACT).

Analysis

The primary analysis in the younger cohort (ages 5 to < 13 year) will be a non-inferiority analysis of mean visual acuity change from enrollment at 16 weeks in the binocular computer treatment group compared with the patching group. The primary analysis in the older cohort (ages 13 to < 17 years) will be a superiority analysis of mean visual acuity change from enrollment at 16 weeks in the binocular treatment group compared with the patching group.

Study Summary Flow Chart

CHAPTER 2: SUBJECT ENROLLMENT

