2.5 Randomization of Eligible Subjects

The Jaeb Center will construct a Master Randomization List using a permuted block design stratified by site and age subgroup (5 to <7 years versus 7 to <13 years) in the younger cohort (5 to <13 years), and stratified by site and baseline amblyopic-eye visual acuity (20/40 to 20/80 (53 to 72 letters) and 20/100 to 20/200 (33 to 52 letters)) in the older cohort (13 to <17 years), which will specify the order of treatment group assignments. Although we would ideally stratify by each of three factors (site, age subgroup, and baseline amblyopic acuity) in both the younger and older cohorts, this was unlikely to achieve the desired balance given the proposed sample size, and so the

2 most important factors were chosen, within each age cohort, for stratification. Randomization will not be stratified by presence of a tropia since diagnosis of a microtropia is problematic.

All eligible subjects enrolled in the study will be randomly assigned in a 1:1 allocation to one of the following groups for each of the age cohorts:

1. Binocular treatment group: binocular computer game play 1 hour per day, 7 days per week (minimum of 4 days per week)
2. Patching group: Patching 2 hours per day, 7 days per week.

Once a child is assigned to treatment, he/she will be included in the analysis regardless of whether or not the assigned treatment is received. Thus, the investigator must not randomly assign a subject to treatment unless convinced that the parent will accept either of the treatments.

CHAPTER 3: TREATMENT AND FOLLOW-UP

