5.2.1 Younger Cohort (Children 5 to <13 years of age)

The standard deviation for change in amblyopic eye visual acuity at 16-weeks was estimated to be 0.15 logMAR from previous ATS studies.³⁷⁻³⁹ The 95% confidence interval for the standard deviation was 0.13 to 0.16 logMAR. These were used to compute sample sizes in the table below:

**Total Sample Size Estimates
Based on 90% Power***

Standard Deviation (logMAR)	Noninferiority Limits (difference in logMAR)			
	0.050	0.055	0.060	0.075
0.13	234	194	164	106
0.14	270	224	188	122
0.15	310	258	216	140
0.16	354	292	246	158

* Based upon alpha = 0.05 for 1-sided t-test. Cells reflect total sample size needed

Based on a standard deviation of 0.15 logMAR, a sample size of 310 subjects was chosen (155 per group) in order to have 90% power for a non-inferiority hypothesis test, assuming that the true difference between the two treatments is zero with a non-inferiority limit of 0.05 logMAR. A total sample size of 346 (173 per group) was computed after adjustment for 10% loss to follow-up.

Interim Monitoring

There are no plans to conduct interim monitoring for efficacy and/or futility given there are no safety concerns or health risks with either treatment, and subjects will have access to the alternate treatment after completing the study. In addition, based on pilot data of binocular therapy in this age group³⁵, it is unlikely that the treatment effect of patching is sufficiently superior to binocular therapy to allow criteria for futility stopping to be met at an interim analysis. Finally, early stopping for efficacy would reduce power for the planned test of superiority of binocular therapy in the event that binocular treatment is declared non-inferior to patching.

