5.3 Primary Analysis

Two treatment approaches will be evaluated within each of the age cohorts as follows:

1. Binocular treatment: Binocular computer game play 1 hour per day, 7 days per week (minimum of 4 days per week)
2. Patching treatment: Patching 2 hours per day, 7 days per week

An analysis of covariance (ANCOVA) will be performed to compute the 16-week mean change in visual acuity for each treatment group, adjusted for baseline acuity and baseline age, and a 95% confidence interval will be constructed on the treatment group difference. Linearity assumptions will be evaluated for baseline visual acuity and baseline age and these factors will be treated as continuous covariates if the model assumptions are met.

For the younger age cohort (5 to <13 years of age), the upper limit of a 1-sided 95% confidence interval on the treatment effect (Patching – Binocular treatment) will be compared with the non-

inferiority limit of 0.05 logMAR. Non-inferiority of binocular treatment will be declared if the upper 1-sided confidence interval limit is less than the non-inferiority margin of 0.05 logMAR. In the event that non-inferiority of binocular treatment is declared, a test for superiority of binocular treatment will be performed using the same 95% confidence interval and pre-specified margin.

For the older age cohort (13 to <17 years of age), superiority of binocular treatment will be declared if the treatment effect (Binocular treatment – Patching) is positive and the 95% confidence interval on the treatment group difference in mean visual acuity change excludes zero.

The primary analysis will follow the intent-to-treat principle. Data will be included only from subjects who complete the 16-week exam within the predefined analysis window. There will be no imputation of data for subjects who are lost to follow-up or withdraw from the study prior to the 16-week exam. In a secondary approach to the primary analysis, multiple imputation for missing data will be performed and results of the analysis with imputation of missing data assessed for consistency with the primary analysis. A separate analysis also will be conducted including only subjects whose outcome exams were performed within the protocol time window for the visit.

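### Younger cohort, secondary binary outcomes: the model in 5.4.1 omits the age stratum used in randomisation, so the reported standard error is somewhat too large and the test mildly conservative

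*Protocol*

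**What the plan says.** Protocol 5.4.1 defines two binary outcomes at 16 weeks. The first is "Amblyopic-eye visual acuity improvement of 2 or more logMAR lines (10 or more letters if E-ETDRS) 16 weeks after randomization". The second is resolution: amblyopic-eye acuity of at least 20/25 (78 letters), and no more than 1 line (5 letters) from the fellow eye. On the model it says: "A p-value for the treatment group comparison will be computed using binomial regression with adjustment for baseline visual acuity". If that model does not converge, the choices are robust Poisson regression or an exact method without baseline adjustment. Proportions are tabulated by treatment group.

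Other sections treat age differently:
- Section 2.5: randomisation is "stratified by site and age subgroup (5 to <7 years versus 7 to <13 years) in the younger cohort".
- Section 1.4: acuity is assessed "using ATS-HOTV for children <7 years at enrollment and the E-ETDRS for children ≥ 7 years at enrollment". Section 2.4 keeps each child on the same test throughout.
- Section 5.3: the primary ANCOVA is "adjusted for baseline acuity and baseline age".
- Section 1.2: both treatments are expected to work less well as children get older, while the difference between them is not expected to depend on age.

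**The concern.** In the younger cohort the age stratum is a design factor and probably a predictor of both outcomes, for two reasons. Section 1.2 expects response to fall with age. The stratum also fixes the measurement scale, and the cut-offs are not quite the same in whole lines as in letters. When randomisation is balanced on a predictive factor that the model then leaves out, the model-based standard error does not credit that balance. It comes out too large, and the test rejects less often than its nominal level allows.

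Section 5.4.1 names its covariates, so this is a stated choice and not a detail left open. It differs from the protocol's own primary model, and no reason is given. At stake is some efficiency in two secondary outcomes, and how their pooled proportions are read.

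**Working it through.** **1. The plan's own figure.** Section 5.2.1 gives the inputs: "Based upon alpha = 0.05 for 1-sided t-test", "in order to have 90% power for a non-inferiority hypothesis test", "The standard deviation for change in amblyopic eye visual acuity at 16-weeks was estimated to be 0.15 logMAR", true difference 0, margin 0.05 logMAR.
- n per group = 2 × (1.645 + 1.282)² × (0.15/0.05)² = 2 × 8.57 × 9 ≈ 154.2, so 155 per group and 310 in total.
- With 10% loss, 155/0.90 = 172.2, so 173 per group and 346 in total.

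Both figures reproduce. No power is stated for the binary outcomes, so 310 completers are used below.

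**2. Do the cut-offs differ?** Section 2.2.1 equates 20/40 to 20/200 (8 lines) with 33 to 72 letters (40 scores), so one line is a band of 5 letters. Assume that ATS-HOTV is scored in whole lines and count over all starting scores:

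| Letters | Gain counts as ≥2 lines | Interocular gap counts as ≤1 line |
|---|---|---|
| 5 | 0% | 100% |
| 6 | 20% | 80% |
| 7 | 40% | 60% |
| 8 | 60% | 40% |
| 9 | 80% | 20% |
| 10 | 100% | 0% |

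In letters, a gain must reach 10 and a gap must not exceed 5. So the 2-line gain and the within-1-line part of resolution are effectively looser in whole lines. The 20/25 part is identical, because 78 letters is the lower edge of the 20/25 band.

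**3. Effect on the 2-line rate.** SD 0.15 logMAR is 7.5 letters. Assume a mean gain of 7.5 letters in every child.
- E-ETDRS, whole letters: P(gain > 9.5) = P(Z > 2/7.5) = 39.5%.
- ATS-HOTV: 50.0%.

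Over SD 6.5 to 8 letters (the interval in 5.2.1) and mean gain 5 to 12.5 letters, the difference is about 9 to 12 points.

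**4. Variance explained by the stratum.** Let f be the share under 7, D the difference in success rate between strata, and p the overall rate. The share of variance is f(1 − f)D² / [p(1 − p)].
- Scale only, f = 0.35, D = 0.10, p = 0.4: 0.2275 × 0.01 / 0.24 = 0.95%. Over the settings in step 3 with f = 0.20 to 0.50, the range is about 0.5 to 1.5%.
- Age also prognostic, f = 0.35, D = 0.20, p = 0.4: 0.2275 × 0.04 / 0.24 = 3.8%.
- f = 0.50, D = 0.30, p = 0.3: 0.25 × 0.09 / 0.21 = 10.7%.

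**5. Power** at 155 per arm, assumed treatment difference 15 points, p = 0.4, f = 0.50, two-sided 5%.
- Without the stratum: SE = √[(0.475 × 0.525 + 0.325 × 0.675)/155] = 0.0550. Power = Φ(0.15/0.0550 − 1.96) = 77.9%.
- With the stratum, subtract 2f(1 − f)D² from the bracket. Power is 78.3% at D = 0.10, 79.6% at D = 0.20 and 81.8% at D = 0.30.

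Over p = 0.3 to 0.5, the gains are under 0.5 point at D = 0.10 and about 1.5 to 4 points at D = 0.20 to 0.30.

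**6. Simulation** of robust Poisson with and without the stratum: N = 310, age-stratified 1:1, f = 0.35, 1,500 trials per setting, treatment effect 2.5 letters for power.

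| Extra mean gain under 7 | Mean SE of log risk ratio, without / with | Power, without / with |
|---|---|---|
| 0 letters | 0.131 / 0.130 | 62.5% / 63.0% |
| 2.5 letters | 0.120 / 0.117 | 58.7% / 61.2% |
| 5 letters | 0.110 / 0.104 | 55.9% / 60.1% |

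In the last row the reported variance falls by 1 − (0.104/0.110)² = 10.6%. With f = 0.50 and 5 extra letters it falls a little more, by 1 − (0.0926/0.0990)² = 12.5%, and power rises from 52.6% to 57.5%. In that setting with no treatment effect:
- the log risk ratio averaged 0.002 in both models;
- its actual spread was 0.0949 without and 0.0948 with the stratum;
- type I error was 3.6% without and 5.2% with it. The Monte Carlo error is √(0.05 × 0.95/1500) = 0.56 point.

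**The case against.** **The scale mismatch does little by itself.** A reader might infer that mixing line and letter cut-offs is what costs precision. Steps 4 to 6 show otherwise: about 1% of variance and under 1 point of power. This objection stands. Any larger gain needs age itself to be prognostic. Section 1.2 supports that in direction but gives no size, so the upper figures rest on assumption.

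**Nothing is biased and no real precision is lost.** A reader might infer that the treatment estimate is distorted or more variable. Stratified randomisation prevents that, and the simulated spread was the same in both models. Only the reported standard error and the p-value are affected, in the conservative direction.

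**Resolution is only partly affected.** Its 20/25 component is the same on both scales, and no power figure was worked out for this outcome. That ATS-HOTV behaves as exact 5-letter bands is also an assumption, because the testing manual is not shown.

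**A richer model may fail to converge.** In a separate check with a log-link binomial model containing both continuous age and the stratum, 91 to 96% of trials converged when gain fell by 0.02 logMAR per year of age, against 100% for the planned model. This argues for adding the stratum alone and for a fallback that keeps it.

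**Context.** These are secondary outcomes without stated power. The primary analysis is continuous and age-adjusted, and 5.4.3 already plans a subgroup analysis by the same age split. Chapter 5 calls itself a summary. That limits the weight of the point but does not remove it, since 5.4.1 does fix the covariate.

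**Conclusion.** The point holds as a modest improvement for the younger cohort's secondary binary outcomes. The planned model omits a factor that the design randomises on, that fixes the acuity test and that the protocol's rationale expects to be prognostic. The cost is a somewhat inflated reported standard error and a mildly conservative test. It ranges from negligible if only the scale differs (about 1% of variance, under 1 power point) to about 4 to 11% of reported variance and 1.5 to 5 power points if age is clearly prognostic. The most extreme simulated setting went slightly beyond the variance range.

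These sizes assume whole-line scoring of ATS-HOTV, 20 to 50% of children under 7, mean gains of 5 to 12.5 letters and, for the upper range, strata 20 to 30 points or more apart.

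A reader might extend the point to the older cohort. The documents do not support that: all those children take E-ETDRS, and baseline acuity, their clinical stratification factor, is already in the model.

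**What to change.** In 5.4.1, for the younger cohort only:
- Fit the binomial model with treatment, baseline acuity and the age stratum (5 to <7 versus 7 to <13 years).
- If it does not converge, use robust Poisson regression with the same covariates.
- If an exact method is still needed, stratify it by the age stratum.
- Tabulate both outcomes by stratum as well as overall, and note which acuity test applies in each. The covariate does not make the two cut-offs equal; the table lets the reader see them.

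The cost is one extra parameter and a slightly higher chance of needing the Poisson fallback; convergence with the stratum alone was not tested. All the data are already collected. If the SAP already specifies the stratum, the protocol wording only needs to be aligned with it.

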5.4.2 Time Course of Visual Acuity Improvement

A secondary analysis will compare treatment groups with respect to the time course of change in visual acuity.

A linear mixed ANCOVA model will be used to compare the rate of visual acuity improvement between the two groups. A regression line will be fit for visual acuity over time for each treatment group and the slope of these lines will be compared by including an interaction term with treatment group and time in the ANCOVA model, adjusted for baseline acuity and main effects of the interaction term. If the interaction term is not statistically significant ($p > 0.05$), then no further

comparisons will be computed. However, if the interaction term is statistically significant, then a comparison of mean visual acuity by treatment group at each time point (0 – baseline, 1 – 4 weeks, 2 – 8 weeks, 3 – 12 weeks, 4 – 16 weeks) will be performed using linear contrasts.

Prior to performing the ANCOVA, the time course of change in visual acuity in each group will be plotted to determine whether data transformation is needed to linearize the relationship between time and visual acuity improvement. In the event that a suitable transformation to linearize the relationship cannot be found, a discrete time model will be used. Exploratory analyses will be conducted to determine the correction structure over time of the data, and to choose a suitable correlation structure for use in the mixed ANCOVA model.

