Regarding study duration, we recognize that the vast majority of available pilot data are from studies of only 4 weeks of treatment duration. Assessing the planned RCT primary outcome at 4 weeks was considered unreasonable because patching may take several months to show the majority of its effect.¹¹⁻¹⁵ On the other hand, assessing the primary outcome after a much longer duration of treatment, such as 6 months, was also considered unreasonable, because some children may be unwilling to play the games for many months.³⁴ Therefore we chose a compromise time point of 16 weeks for the primary outcome assessment, with planned secondary comparisons at 4, 8, and 12 weeks.

Regarding the dose of binocular treatment, pilot studies in adults by Hess et al^{27, 32} primarily used one hour per day, whereas the pilot studies by Birch et al³⁵ in children used 4 hours a week. We therefore propose to prescribe “one hour a day, 7 days a week,” with a minimum of 4 days for children unable to play 7 days a week.

Regarding choice of specific games to be used during the proposed study, game development has continued for the Hess Falling Blocks game, creating 3 levels of difficulty to allow play by children as young as 5 years, but with more difficult levels that will still engage teenagers. Because this game for binocular treatment is currently available with multiple levels of difficulty, and most available pilot data are with this binocular game, we plan to use only the Hess Falling Blocks game in the proposed RCT.

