5.4.3 Subgroup Analysis

The treatment effect in subjects based on baseline factors will be assessed in exploratory analyses. Analyses of subgroups will be considered exploratory and used to suggest hypotheses for further investigation in future studies.

The subgroups of interest include the following: amblyopic-eye visual acuity, age (in younger cohort only), the presence of a tropia, and prior amblyopia treatment.

In accordance with NIH guidelines, a subgroup analysis of treatment effect according to gender, as well as race/ethnicity, will be conducted. However, based on results from previous ATS studies, a differential treatment effect by these variables is not expected.

The general approach for these exploratory analyses will be to conduct an analysis of covariance similar to the primary analysis including an interaction for treatment and the subgroup covariate of interest. If the overall F-test for interaction is not statistically significant ($p > 0.05$), then no subgroup comparisons will be computed, but this will not be interpreted as conclusive evidence of no subgroup effect given that power for the tests of interaction is low.

The subgroup definitions for the planned subgroup analyses are as follows:

1. Amblyopic-eye visual acuity at baseline (20/40, 20/50, 20/63, 20/80 or worse)
2. Presence of a heterotropia at baseline (yes/no)
3. Age (years) at baseline (5 to <7, 7 to <13)
4. Prior amblyopia treatment (yes/no)

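### The week 4, 8 and 12 comparisons planned in section 1.2 are made conditional in section 5.4.2 on a slope test that has almost no power for an early difference that closes by week 16

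*Protocol*

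**What the plan says.** Protocol section 1.2 explains week 16 as a compromise between the 4-week span of most pilot data and a much longer follow-up. It pairs that choice "with planned secondary comparisons at 4, 8, and 12 weeks", with no condition attached.

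Section 5.4.2 sets the analysis. A regression line is fitted to acuity over time in each arm, and "the slope of these lines will be compared by including an interaction term with treatment group and time in the ANCOVA model". The model is "adjusted for baseline acuity and main effects of the interaction term". The rule follows: "If the interaction term is not statistically significant ($p > 0.05$), then no further" comparisons are made. "However, if the interaction term is statistically significant, then a comparison of mean visual acuity by treatment group at each time point" is carried out, with the time points given as "0 – baseline, 1 – 4 weeks, 2 – 8 weeks, 3 – 12 weeks, 4 – 16 weeks) will be performed using linear contrasts".

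The same section says that the time course is plotted before the model is fitted, that time or outcome may be transformed to straighten the relationship, and that a discrete time model is used if no suitable transformation is found.

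**The concern.** The two sections cannot both be followed. One plans three visit comparisons; the other withholds all of them after a non-significant slope test. The protocol fixes this rule itself, so it is not a detail left to a later analysis plan.

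The chosen gate is also poorly matched to the question. A difference in slope over weeks 0 to 16 measures steady divergence. If one arm improves sooner and the other catches up, the fitted slopes can be nearly equal although the arms differ clearly at week 4.

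The protocol gives reasons to expect that this could happen. Section 1.2 says that patching may need several months for most of its effect, while the pilot results for the binocular game come mainly from 4 weeks of treatment. Section 5.2.1 sizes the younger cohort on a true difference of zero at week 16. At stake is whether the trial reports speed of response, which the interim visits are there to show.

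A separate and smaller fault is that baseline acuity is a covariate and also, as time 0, a time point at which the arms are contrasted.

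**Working it through.** **Inputs from the protocol.** Younger cohort (section 5.2.1): SD of 16-week change 0.15 logMAR, 155 evaluable per arm, margin 0.05 logMAR, true difference 0, one-sided alpha 0.05, power 90%. Older cohort (section 5.2.2): SD 9 letters, 70 per arm, difference 5 letters. Visits are coded 0 to 4 (section 5.4.2).

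**Assumptions not in the protocol.** The within-child covariance, the shape of the treatment difference over time, complete data, and 0.02 logMAR per letter.

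**1. The plan's own sample size.** n per arm = 2 × (1.645 + 1.282)² × (0.15/0.05)² = 2 × 8.57 × 9 ≈ 154.2, so 155 per arm and 310 in total. This agrees with section 5.2.1.

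**2. What the slope test sees.** The least-squares slope over times 0 to 4 weights the five visits by (t − 2)/10, that is −0.2, −0.1, 0, 0.1, 0.2. For a difference d:
- d at weeks 4 and 8, d/2 at week 12, nil at week 16: −0.1d + 0.05d = −0.05d per visit.
- d at weeks 4, 8 and 12, nil at week 16: −0.1d + 0.1d = 0.
- d at every visit after baseline: −0.1d + 0.1d + 0.2d = 0.2d per visit.

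**3. How often the gate opens, by hand, in one simple case.** Take a random intercept with independent residuals. The variance of change is twice the residual variance, so the residual variance is 0.15²/2 = 0.01125. The slope variance per child is 0.01125/10 = 0.001125. The SE of the slope difference is √(2 × 0.001125/155) = 0.00381. The two-sided 0.05 test then gives:

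| Difference at weeks 4, 8, 12, 16 (logMAR) | Slope difference | Ratio to SE | Gate opens |
|---|---|---|---|
| 0.05, 0.05, 0.025, 0 | −0.0025 | 0.66 | 10% |
| 0.05, 0.05, 0.05, 0 | 0 | 0 | 5% |
| 0.04, 0.03, 0.02, 0 | −0.0020 | 0.52 | 8% |
| 0.05 throughout | 0.0100 | 2.62 | 75% |
| 0.04 throughout | 0.0080 | 2.10 | 56% |

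**4. The direct week-4 test.** Without baseline adjustment, and with the SD of change at week 4 also taken as 0.15, the SE is 0.15 × √(2/155) = 0.0170. Power is about 65% for 0.04 (0.04/0.0170 = 2.35) and about 83% for 0.05 (0.05/0.0170 = 2.93). Adjusting for baseline raises both.

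**5. Other covariances** (random intercept, random intercept and slope, AR(1), each scaled to the protocol's SD):
- Closing patterns as in the first three rows: gate 4–10%; direct week-4 ANCOVA 72–100%.
- A 0.05 difference at week 4 only: gate 5–26%.
- Sustained difference of 0.04–0.05: gate about 51–83%.
- Older cohort, 5 letters: first closing pattern 5–11%, sustained 77–90%, direct week-4 test 95–100%.

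**6. The two safeguards in section 5.4.2.** With square-root or log time, the gate opens for closing patterns about 5–75% of the time over one set of covariances, and up to 96% over a wider set of shapes and covariances. A joint 4-degree-of-freedom test, standing in for the discrete time model, opens it 64–82% of the time for the 0.04, 0.03, 0.02, 0 pattern and 84–100% for early differences of 0.05.

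**7. Baseline used twice.** At time 0 the outcome and the covariate are the same number, and the contrast compares randomised arms before treatment. In complete balanced data the slope-interaction estimate is the same with and without the covariate (difference below 1e-15).

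**The case against.** The strongest reply is that section 5.4.2 is not tied to a straight line. Curvature is looked for first, and a discrete time model would usually detect an early difference. This has force, but the discrete model is reached only if no transformation is judged suitable. Where gains are 0.09, 0.12, 0.14, 0.15 in one arm and 0.05, 0.09, 0.12, 0.15 in the other, square-root time fits the arm means with R² of 0.99 and 0.97, so a transformation would probably be accepted. Whether the planned comparisons appear then depends on a choice made after seeing the data.

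Three stronger readings are tempting, and the protocol does not support them.

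- *Early differences in general will usually go unreported.* A difference that appears by week 4 and lasts usually opens the gate when week 0 is in the model, as the plan lists it. A figure near 5% for a constant difference arises only if the week-0 row is dropped and a slope is still fitted. That other model would also open the gate 67–87% of the time for the 0.04, 0.03, 0.02, 0 pattern, so no single slope model misses both.
- *The double use of baseline causes the loss.* The interaction estimate does not change with the covariate, so this is a separate defect.
- *Section 5.4.3 has the same fault.* It says that "a subgroup analysis of treatment effect according to gender, as well as race/ethnicity, will be conducted" and that without a significant interaction "then no subgroup comparisons will be computed". But the interaction test is itself the analysis conducted. The section calls these analyses exploratory, admits low power, and bars reading non-significance as proof of no subgroup effect. That is a defensible trade-off.

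It is also true that this is a secondary analysis, that the 16-week primary comparison is untouched, and that the time courses are plotted in any case.

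**Conclusion.** The point holds for section 5.4.2. Section 1.2 plans the week 4, 8 and 12 comparisons outright, and section 5.4.2 makes them depend on a test that is close to blind to one plausible pattern. For a difference that closes by week 16, the linear gate opens about 4–10% of the time, against 72–100% for a direct week-4 ANCOVA. A sustained difference of 0.04–0.05 logMAR opens it about 51–83% of the time.

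The size of the loss rests on the assumed covariances and shapes, since the protocol gives neither within-child correlations nor expected trajectories for the two arms. The conflict between the two sections, and the emptiness of the time-0 contrast, need no such assumptions. The change should be made, but nothing in the primary analysis depends on it.

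**What to change.** Change section 5.4.2 only:
- Fit visit as a category (4, 8, 12 and 16 weeks) with a treatment-by-visit term and baseline acuity as a covariate only.
- Remove time 0 as an outcome and as a contrast.
- Report the adjusted treatment difference with its 95% confidence interval at every visit, whatever the interaction p-value, labelled as secondary and not adjusted for multiplicity.

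Removing the week-0 row while keeping the slope gate is not enough. The slope over weeks 4 to 16 is zero for a sustained difference, and the gate would then open only 5% of the time.

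The cost is wording and table shells, with no new data and no change in sample size. The downside is a few more intervals that are not adjusted for multiplicity and must be read as such.
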